10.4.1 The Last Observation Carried Forward

For the binary endpoints, missing data will be handled by the LOCF approach.

10.4.2 Mixed Model Repeated Measures

For the change from baseline in BCVA, a mixed model repeated measures (MMRM) will be employed. The MMRM model will include treatment, visit (as a categorical variable), surgical group, baseline BCVA, treatment-by-visit interaction, and baseline BCVA-by-visit interaction.

An unstructured covariance matrix will be used for the within-subject correlation. The Kenward-Roger approximation will be used to estimate denominator degrees of freedom. In case of a convergence failure with the unstructured covariance, the following structures will be assessed in a sequential fashion until convergence is achieved: heterogeneous Toeplitz, Toeplitz, heterogeneous auto-regression, and auto-regression (See sample SAS code in Appendix 6).

10.4.3 Multiple Imputation Based on Missing Not at Random

For the change from baseline in BCVA, the pattern-mixture model using a control-based multiple imputation method will be performed based on missing data not at random for the ITT population. The method described here is based on methodology described by Little and Yau (1996) and extended in Ratitch and O'Kelly (2011). It assumes that subjects who discontinue from the study would have the same evolution of the disease as those subjects on the control group who remained in the study. The assumption that efficacy profiles of dropouts after discontinuation are similar to those of untreated control subjects is considered conservative because this methodology tends to minimize the difference between treatment and control groups. If the results of this analysis are in line with the primary efficacy results, then it can be confidently concluded that the primary analysis results are robust.

Biogen / NightstaRx,	Ltd
BIIB111	

Using this method, missing data after discontinuation will be imputed based on control group data using multiple imputation methodology for all subjects (including treatment subjects).

The steps to implement this sensitivity analysis are as follows (See sample SAS code in Appendix 7):

- 1. 100 datasets will be generated where missing data at intermediate visit(s) will be imputed for each treatment group using non-missing data from all subjects within the treatment group by a Monte Carlo Markov Chain (MCMC) imputation model using the MCMC statement in the SAS PROC MI procedure. As a result, each dataset will only have missing ending data, or a monotone missing data pattern.
- 2. For each dataset from Step 1, missing ending data will be imputed based on information from the control group. As a result, 100 imputed complete datasets will be generated.
 - Missing data at the first post-baseline visit will be imputed by a regression imputation model using the SAS PROC MI procedure with the REGRESSION option in the MONOTONE statement.
 - The SAS PROC MI procedure will use data from all control subjects as well as treatment subjects with missing data at the visit (i.e., only those that need imputation at the visit). Because subjects from treatment groups without missing data at the visit are excluded from this step, they will not contribute to the estimation of the imputation model for the visit.
 - The same process will be used for all other visits. Subjects whose missing data were imputed at previous visits will contribute to the imputation for the next visit.
 - The regression imputation model includes an intercept and the slopes of the measurements from all previous visits.
- 3. Analyze each imputed complete dataset.
- 4. Combine estimates from the results of each model.

10.5 Other Secondary Efficacy Endpoints

For the analysis of the following efficacy endpoints, the same analysis of covariance (ANCOVA) model will be utilized based on the ITT population with missing data handled by the LOCF approach.

- Change from Baseline in BCVA at Months 4, 8 and 12
- Change from Baseline at Month 12 in:
 - Total Area of Preserved AF
 - Distance from Foveal Center (FC) to nearest Border of Preserved AF
- Change from Baseline in the following SD-OCT variables at Month 12:
 - Foveal Subfield Thickness
 - Total Macular Volume
 - Central Horizontal Ellipsoid Width

- Central Ellipsoid Area
- Choroidal Thickness
- Change from Baseline in the following microperimetry variables at Month 12:
 - Mean Sensitivity
 - Bivariate Contour Ellipse Area 63%
 - Bivariate Contour Ellipse Area 95%
- Change from Baseline in contrast sensitivity score at Month 12
- Change from Baseline in colour vision at Month 12
- Change from Baseline in reading speed test at Month 12
 - The reading speed will be calculated using the following formula: [number of words in the text number of misread words] / reading time x 60. The number of words per text is available in Appendix 1: IRest Reading Speed Test, Conversion Table, while the number of misread words and reading time will be collected in the case report form (CRF).
- Change from Baseline in the 25-item VFQ-25 overall score and sub-scale scores at Month 12
 - The VFQ-25 patient questionnaire consists of 25 vision-related questions, each of them pertaining to one of the 11 vision-related subscales. For each subscale, a score is calculated. Scores are between 0 and 100, where a higher value represents better functioning. The overall composite score is calculated as the mean of the sub-scale scores (Mangione 2000).

CONFIDENTIAL

CONFIDENTIAL

Page 27 of 46

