7 INVESTIGATIONAL PLAN

7.1 Overall Study Design

This is an outcomes-assessor-masked, prospective, randomised, parallel-controlled group, multi-centre, global, interventional Phase 3 study, consisting of 8 visits with a 12-month evaluation period. A study schematic is presented below.

Figure 1 Overall Study Schematic

During the Screening/Baseline period (Visit 1), each subject will be assessed for eligibility. If a subject has only 1 eligible eye, that eye will be designated as the "study eye" and the subject's other (non-eligible) eye will be designated as the "fellow eye." If a subject has 2 eligible eyes, the selection of the "study eye" will be made on clinical grounds and will generally be the worse eye affected. This will be discussed in detail and agreed with each subject as part of the informed consent process. Subject choice will be considered in cases where the degeneration is relatively symmetrical between the two eyes.

During the Screening/Baseline period, eligible subjects will be randomised in a 2:1:2 ratio to either the AAV2-REP1 high-dose group $(1.0 \times 10^{11} \text{ gp})$, the AAV2-REP1 low-dose group $(1.0 \times 10^{10} \text{ gp})$ or the untreated Control group. To facilitate understanding of the study design, eyes will be classified into 4 categories based on treatment-group assignment and designation of study/fellow eye: AAV2-REP1-study eye (includes high and low dose); AAV2-REP1-fellow eye (includes high and low dose); Control-study eye; and Control-fellow eye. Once a subject has been randomised, a change in "study eye" designation is not permitted.

At the time of randomisation, a projected surgical date should be defined for each subject. For each subject randomised to the control group, this projected surgical date (+/-1 day) should remain the Day 0 (Visit 2) date. For each subject randomised to a treated group, Day 0 (Visit 2) will be the actual date of surgery. The Screening / Baseline period must occur within 8 weeks prior to dosing (Week 2, Day 0).

On this visit (Visit 2, Day 0), subjects in the AAV2-REP1-treatment groups will undergo vitrectomy and retinal detachment before receiving a sub-retinal injection of AAV2-REP1 high dose (1.0×10^{11} gp), or AAV2-REP1 low dose (1.0×10^{10} gp) in their study eye (i.e., AAV2-REP1-study eye).

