11.1 VFQ-25 Questionnaire

Subjects will complete the VFQ-25 at the times indicated in Table 3. The VFQ-25 must be completed by the subject at the beginning of the study visit, before any significant interaction with the study staff.

This questionnaire measures dimensions of self-reported vision-targeted health status that are most important to persons with eye disease (Mangione 2001). Improvement in the VFQ-25 will be evaluated using individual scores, subscale scores, and the overall composite score. The VFQ-25 will only be conducted in languages in which a validated translation is available.

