13.6 Efficacy Analyses

Statistical tests will be performed at the alpha level of 0.05 (unless otherwise specified). Statistical tests and 95% CIs will be 2-sided.

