3.6 Sample Size

Approximately 160 subjects will be enrolled in the study (64, high dose group; 32, low dose group; 64, control group).

The sample size calculation is based on a Fischer's exact test. CHM is a degenerative disease, it is therefore assumed that a \geq 15 letter BCVA gain would not be observed in subjects without CHM treatment. Assuming that 16.7% of the treated subjects will gain \geq 15 letters BCVA at Month 12, 56 subjects in the high dose group and the control group provide at least 90% power at a 0.05 level of significance with a 2-sided test. To be conservative, 64 patients in the high dose group and 64 patients in the control group are needed to ensure 85% power in case 1 patient in the untreated control group has \geq 15 letter BCVA gain by chance, which corresponds to a total of 160 patients completing the study.

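### VFQ-25 is one score per person, only the study eye is treated, and SAP 10.5 uses no fellow-eye information, so a null VFQ-25 result would be hard to interpret.

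*SAP*

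**What the plan says.** - **Instrument.** Protocol 11.1 describes VFQ-25 as a self-report: "This questionnaire measures dimensions of self-reported vision-targeted health status". SAP 10.5 scores it as sub-scales and one composite per patient. There is no score by eye.
- **Treated eye.** SAP 3.2 gives the injection to the study eye only. With two eligible eyes, Protocol 7.1 says the choice "will be made on clinical grounds and will generally be the worse eye affected". With one eligible eye, that eye is used. Because eligibility is 34 to 73 letters, the other eye may then be better or worse.
- **Analysis.** SAP 10.5 plans "Change from Baseline in the 25-item VFQ-25 overall score and sub-scale scores at Month 12" with the same ANCOVA as its other continuous endpoints, in the ITT population with LOCF. SAP 10.2 gives the terms: surgical group, baseline value and arm. Protocol 13.6.3 adds Age and Race for the VFQ-25 composite; SAP 10.5 does not show them.
- **Fellow eye.** BCVA is assessed in both eyes (Protocol 11.3). The study-eye versus fellow-eye analyses in SAP 10.1 and 10.2 cover the primary and key secondary BCVA endpoints only. The subgroups in SAP Section 12, Table 2, do not include whether the study eye was the better or the worse eye.
- **Status.** VFQ-25 is an other secondary endpoint. It lies outside the hierarchy in SAP 10.3 and has no power statement.

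**The concern.** BCVA measures the treated eye directly. VFQ-25 measures the person, who also has an untreated eye that will often see better. If daily visual function depends more on the better-seeing eye, part of a real gain in a worse study eye will not reach the score.

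What is at stake is interpretation. VFQ-25 is the visible patient-reported endpoint in the secondary list. As planned, a null result would fit two quite different explanations: the treatment did nothing that subjects notice, or it helped an eye they rely on less. No planned and visible analysis would help to tell these apart, although the BCVA needed to do so is collected in both eyes.

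**Working it through.** **1. The plan's own figures.** They concern the primary BCVA endpoint only. The SAP says "56 subjects in the high dose group and the control group provide at least 90% power at a 0.05 level of significance", at 16.7% versus 0%. With 56 per arm and no control responder, Fisher's exact test is significant from 6 high-dose responders (p = 0.027; 5 responders give p = 0.057). The probability of 6 or more from a binomial with n = 56 and rate 0.167 is 92.3%, so the statement holds. With 64 per arm and exactly 1 control responder, 8 are needed (p = 0.033; 7 give p = 0.062), and the probability is 85.9%, against a stated 85%. Neither figure bears on VFQ-25.

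**2. What the documents give for VFQ-25.** They give arm sizes (64, 32, 64) and a two-sided 0.05 level. They give no effect, SD or power, and no share w of subjects whose study eye is the worse eye. The number analysed may also be below 64 per arm, since the questionnaire is used only where a validated translation exists (Protocol 11.1).

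**3. Illustration of the mechanism.** Assumptions, none from the documents: standardised effect 0.5 in subjects who can show it, no effect at all when the study eye is the worse eye, equal SDs, 64 versus 64. The mean effect is 0.5 × (1 − w). The t-test has 126 degrees of freedom and noncentrality 0.5 × (1 − w) × √(64/2).

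| w | Diluted effect | Power |
|---|---|---|
| 0 | 0.50 | 80% |
| 0.1 | 0.45 | 71% |
| 0.2 | 0.40 | 61% |
| 0.3 | 0.35 | 50% |
| 0.5 | 0.25 | 29% |
| 0.7 | 0.15 | 13% |
| 0.9 | 0.05 | 6% |
| 1 | 0 | 5% (the test level) |

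The answer runs from no loss to total loss, depending on a w that nobody can read from the documents. Zero transfer from a worse eye is also the extreme case.

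**4. The starting point is arbitrary too.** Suppose only the planned 16.7% of treated subjects improve, each by an assumed 10 points. The mean difference is 0.167 × 10 = 1.67 points. Even with no dilution, power is 22% at an assumed SD of 8 and 10% at an assumed SD of 15. With 20 points it is 3.34 points, and power is 65% and 24%. The 80% in the first row of the table is therefore no benchmark.

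**5. What a fellow-eye covariate can do.** It lowers residual variance by the square of its partial correlation with the outcome, given the terms already in the model. Simulation under assumed correlations gave a reduction of about 0 to 10%; the upper end corresponds to a partial correlation of √0.10 ≈ 0.32. The gain is modest because baseline VFQ-25 is already in the model. The covariate improves precision but does not undo dilution; only the estimate by eye status addresses that.

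**The case against.** The strongest case is that the planned comparison is valid and answers a legitimate question. The study eye is chosen before randomisation in every arm (Protocol 9.5), so eye choice cannot bias the arms against each other. A person-level effect is a sensible thing to estimate. VFQ-25 carries no confirmatory weight. All of this stands.

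Three stronger readings are tempting, and the documents do not support them.

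- **A reader might infer that VFQ-25 follows the better eye, so treating a worse eye cannot register.** Protocol 11.1 says only that it is a self-report of vision-related health. Nothing says how the two eyes combine. Protocol 7.1 foresees subjects with fairly symmetrical degeneration, in whom a 15-letter gain could make the study eye the better one. Where the only eligible eye is the better eye, the score may be sensitive.
- **A reader might take the lower rows of the table as the trial's VFQ-25 power.** They combine an arbitrary effect, zero transfer and an unknown w.
- **A reader might infer that fellow-eye progression adds material noise.** SAP 5.5 expects very slow progression and cites an average loss of 0.5 letters over 20 months in the natural history study. A baseline covariate would not capture later progression in any case.

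Two further limits stand. Subjects know whether they were treated (Protocol 14.1), so self-report bias could inflate a VFQ-25 effect as easily as dilution could hide one. Parts of the SAP are not visible: Section 10.6 is listed in the contents but absent, and the sentence introducing the subgroup table is cut. A relevant analysis there cannot be excluded.

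**Conclusion.** The point holds as a cheap improvement to an other secondary endpoint. It is not a flaw in the trial's main inference. The design facts are documented: one treated eye, generally the worse when both qualify; one score per person; no visible use of the fellow eye. The comparison is unbiased with respect to eye choice.

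That a null would be ambiguous rests on one assumption from outside the documents, namely that self-reported function depends more on the better-seeing eye. If that is so, the study-eye effect is diluted by an amount that cannot be computed from what is given. If it is not, little is lost by the plan as written.

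The mismatch between Protocol 13.6.3 and SAP 10.5 on Age and Race does not depend on this assumption and needs settling either way.

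**What to change.** In SAP 10.5, for VFQ-25, before database lock:

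1. **Supportive estimate by study-eye status.** Pre-specify high dose versus control by whether the study eye's baseline BCVA is equal to or better than the fellow eye's, or worse. Use an arm-by-status interaction and report both estimates. Class a fellow eye with no letter score as the worse eye. This rule is needed because Protocol 11 lets a procedure be skipped in an eye with poor vision, and Protocol 11.3 moves eyes that read no letters to finger counting, hand movements or light perception.
2. **Covariate.** Add baseline fellow-eye BCVA to the VFQ-25 model, scoring no readable letters as 0.
3. **Reconcile the model.** State whether Age and Race are in the composite model, so that Protocol 13.6.3 and SAP 10.5 describe the same analysis.

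The cost is SAP wording and one extra model, with no new data collection. The downsides are that one stratum may be small and its estimate imprecise, and that the covariate's gain is likely small. A sentence of interpretation alone would be a weaker remedy, because it gives the reader no estimate with which to separate the two explanations of a null result.

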11 SAFETY ANALYSIS

All analyses of safety data will be performed using the safety population. All analyses of safety data will be presented using descriptive summary text. No inferential analyses of safety data will be needed.

11.1 Adverse Events

Treatment-emergent adverse events (TEAEs) are defined as adverse events starting on or after the day of the surgery (or, for control subjects, Visit 2, Day 0). A pre-existing event that worsens in severity after Day 0 is treated as a new TEAE with date of onset set to the date of the increased severity. Summary tables will include TEAEs only. TEAEs will be summarized by eye (study eye vs non-study eye) for ocular events, by treatment (low dose, high dose and untreated control) and overall. Non-treatment emergent AEs will be listed only.

An ocular event is an event where the site of the event is reported as both eyes (OU), right eye (OD) or left eye (OS).

Proportion of subjects reporting an event will be calculated based on the number of subjects in the corresponding treatment group. The 95% CI will be calculated using the Clopper-Pearson method.

The number and percentage of subjects reporting any event, any non-ocular event, any ocular event, any ocular event in the study eye and any ocular event in the non-study eye will be summarized.

The summary of overall AEs (or SAEs) will be limited to TEAEs. All AEs will be coded using Medical Dictionary for Regulatory Activities (MedDRA) version 21.1 or higher.

An overall summary table of TEAE by treatment will be provided for the following categories:

- Number and percentage of subjects with a TEAE
- Number and percentage of subjects with a treatment-related TEAE
- Number and percentage of subjects with a serious TEAE
- Number and percentage of subjects with a treatment-related serious TEAE
- Number and percentage of subjects with a TEAE leading to death
- Number and percentage of subjects who discontinued due to a TEAE
- Number and percentage of subjects with a TEAE by severity
- Number and percentage of subjects with a TEAE by outcome
- Number and percentage of subjects with a TEAE by action taken

Adverse events will be summarized by treatment group and overall for subjects in the safety population. The following summaries of TEAEs will be provided:

- TEAEs by SOC and PT
- TEAEs by SOC and PT reported in \geq 5% in any treatment group

Biogen /	NightstaRx,	Ltd
RIIR111		

- TEAEs by SOC, PT, and maximum severity (missing severity, if any, will be counted as severe).
- Treatment-related (study drug or study procedure) TEAEs by SOC and PT
- Study procedure-related TEAEs by SOC and PT
- Study drug-related TEAEs by SOC and PT
- Serious TEAEs by SOC and PT
- Treatment-related (study drug or study procedure) serious TEAEs by SOC and PT
- Study procedure-related serious TEAEs by SOC and PT
- Study drug-related serious TEAEs by SOC and PT
- TEAE leading to death by SOC and PT

In the summary, subjects may be counted under multiple SOCs and PTs, but for each SOC and PT, subjects are only counted once. If a subject experiences the same AE at more than one severity, the most severe rating will be given precedence.

If a subject experiences the same AE at more than one relationship to study drug/procedure, causal relationship will be given precedence over no causal relationship. However, where a causal relationship is identified by the Investigator, the subject will be counted once within each sub-category (related to Study Drug, related to Study Procedure, related to both Study Drug and Study Procedure unknown). In the summary tables, related events are defined as events that are assessed by the investigator to be related to study drug/procedure/both or with an unknown relationship.

Separate additional summaries will be provided for adverse events classified as Ocular Inflammation and Visual Acuity Reduced. The lists of PTs assigned to Ocular Inflammation and Visual Acuity Reduced are provided in a separated document (BIIB111 Signal Detection Plan). The following summaries will be provided by treatment:

- Ocular Inflammation-related TEAEs by SOC and PT
- Ocular Inflammation-related TEAEs by SOC and PT, and by time to onset (≤30 days; >30 days)
- Visual Acuity Reduced-related TEAEs by SOC and PT
- Visual Acuity Reduced-related TEAEs by SOC and PT, and by time to onset (≤30 days; >30 days)

Imputation rules for partial dates are presented in Appendix 3.

Summaries presenting frequency of AEs by SOC and PT will be ordered by descending frequency of SOC in the High Dose group and then, within a SOC, by descending frequency of PT in the High Dose group.

The following listings will be provided:

- All AEs
- AEs reported by subjects who discontinued from the study due to an AE
- All SAEs

• AEs leading to death

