9.8 Concomitant Therapy

Subjects cannot have participated in another research study involving an investigational product in the past 12 weeks or received a gene/cell-based therapy at any time previously.

Throughout the study, subjects may be prescribed any concomitant medications, procedures, and/or treatments deemed necessary. Details of concomitant medications, procedures, and treatments will be collected at the Screening/Baseline Visit and updated at every study visit (including the ET Visit, if applicable). Concomitant medications, procedures and treatments (including corticosteroids) taken during the study are to be recorded in the subject's medical records and eCRF; an exception to this is any medication used in the course of conducting a study assessment (e.g., ophthalmic dyes, topical anaesthesia, dilating eye drops).

To minimise inflammation resulting from surgery and potential or unexpected immune responses to vector/transgene, all subjects who receive AAV2-REP1 will be given a 21-day course of oral corticosteroid (e.g., prednisolone/prednisone), modified from the 17-day protocol established in the voretigene neparvovec-rzyl AAV gene therapy clinical trial for treatment of patients with confirmed biallelic RPE65 mutation-associated retinal dystrophy (Maguire 2008), allowing an extra 4 days for tapering the dose at the end of the course. Hence, this will be 1 mg/kg/day prednisolone/prednisone for a total of 10 days, (beginning 2 days before the vector injection, on the day of injection, and then for 7 days), followed by 0.5 mg/kg/day for 7 days, then 0.25 mg/kg/day for 2 days and 0.125 mg/kg/day for 2 days (21 days in total). Weight captured at Visit 1 (Screening/Baseline) will be used to calculate the required dose during the 21-day course, and all doses should be rounded to the nearest 1 mg. Compliance with the use of corticosteroid (e.g., prednisolone / prednisolone / prednisolone / prednisolone / prednisolone) will be captured in a patient diary card and in the eCRF.

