13.7.1 Adverse Events

AEs will be coded using the Medical Dictionary for Regulatory Affairs version 21 or higher. Events will be summarised by system organ class, preferred term, and group. Both the number of eyes/subjects experiencing an AE and the number of events will be summarised. Similar summaries will be produced for study drug/procedure-related AEs, AEs leading to discontinuation, and SAEs. AEs will also be summarised by maximum severity, relationship to study drug/procedure, and time to onset and resolution.

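### Adverse-event tables start on the day of surgery, but the required steroid course starts two days earlier in treated subjects only, so onsets in those two days get no by-arm rate.

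*SAP*

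**What the plan says.** SAP 11.1 sets the start of the treatment-emergent window: "Treatment-emergent adverse events (TEAEs) are defined as adverse events starting on or after the day of the surgery". The untreated arm has its own anchor in place of an operation date: "or, for control subjects, Visit 2, Day 0". Three further statements in that section fix what is tabulated: "Summary tables will include TEAEs only"; "The summary of overall AEs (or SAEs) will be limited to TEAEs"; and, for everything else, "Non-treatment emergent AEs will be listed only". There is one route back into the tables: "A pre-existing event that worsens in severity after Day 0 is treated as a new TEAE".

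Protocol 9.8 requires a 21-day oral corticosteroid course in all subjects who receive AAV2-REP1. The first ten days are at the highest dose level, "beginning 2 days before the vector injection, on the day of injection, and then for 7 days". The corticosteroid footnote to Table 3 in Protocol 17.1 confirms that the course is for treated subjects only and times its start from the planned surgical date.

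Protocol 12.3.2 collects AEs from informed consent, so events on Days -2 and -1 are in the database. Protocol 13.7.1 plans AE summaries by group ("Both the number of eyes/subjects experiencing an AE and the number of events will be summarised") and does not mention a treatment-emergent restriction. Protocol 13 leaves the details of analysis to the SAP.

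**The concern.** What a patient in a treated arm undergoes is steroid, then surgery, then vector. The AE tables that compare arms begin at the second of these. In the two days before, only treated subjects are exposed to anything the protocol requires, so an event caused by the steroid in those days can be missed in the treated arms and has no counterpart in control.

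The by-arm tables matter more than usual for the steroid. Under Protocol 12.3.2 a related event is attributed to study medication, study procedure, both or unknown, and there is no steroid category. SAP 9.3 summarises steroid use separately, but that describes exposure and not harm. A comparison of AE rates between arms is therefore the main place where a steroid effect could show. At stake is the completeness of the harm profile of the regimen; no efficacy result is affected.

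**Working it through.** **Inputs**
- Steroid course (Protocol 9.8): 2 days before injection, the injection day and 7 days after at 1 mg/kg/day; then 7 days at 0.5, 2 days at 0.25 and 2 days at 0.125 mg/kg/day.
- Planned arms (Protocol 13.1): 64 high dose, 32 low dose, 64 control.
- Window start (SAP 11.1): day of surgery, or Visit 2 (Day 0) for controls.

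**Reproducing the stated course length**
- (2 + 1 + 7) + 7 + 2 + 2 = 21 days, as the protocol states.

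**Part of the course before the window opens**
- By days: 2/21 = 9.5%. The other 19 days are inside the window.
- Cumulative planned dose: 10 × 1 + 7 × 0.5 + 2 × 0.25 + 2 × 0.125 = 14.25 mg/kg.
- By dose: 2/14.25 = 14.0%.
- At the planned size: (64 + 32) × 2 = 192 subject-days of required steroid in the treated arms, against 0 in control.

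These figures measure exposure, not missed events.

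**How many events could be involved**

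The documents give no AE rate for these days, so the rates p below are assumptions. The expected number of treated subjects with an onset is 96p, and the chance of at least one is 1 − (1 − p)^96.

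| Assumed p | Expected subjects of 96 | Chance of at least one |
|---|---|---|
| 0.5% | 0.5 | 38% |
| 1% | 1.0 | 62% |
| 2% | 1.9 | 86% |
| 5% | 4.8 | 99% |

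**Effect on a table row**

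One omitted subject lowers a row by 1/64 = 1.6 percentage points in the high-dose arm or 1/32 = 3.1 points in the low-dose arm. This holds only if he has no other treatment-emergent event in that row. If he has one, the row does not move.

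**What happens to an event that starts on Day -2 or -1**

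| Event | Handling under the SAP |
|---|---|
| Exact onset date, resolves or persists unchanged | Listings only |
| Exact onset date, worsens after Day 0 | Tabulated as a new event (11.1) |
| Start day missing, same month as treatment | Set to the treatment start date and tabulated, unless it clearly ended before (Appendix 3) |
| Leads to withdrawal from the study | Withdrawal can show in disposition by reason (Section 6) |
| Subject never receives vector | Outside the safety population (7.2), so in no safety table |

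**The case against.** The surgery-day anchor is defensible. The protocol places the steroid under concomitant therapy, not under treatments administered, and defines AEs and relatedness by study medication and surgical procedure. The SAP uses the same anchor for study day, for prior and concomitant medication, and for time to discontinuation. The rule applies to all arms and also leaves out control events before Day 0. All of this stands, and it is a reason to leave the definition alone.

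A reader might infer three stronger things that the documents do not support.

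- *The SAP contradicts the protocol.* It does not. Protocol 13.7.1 sets no onset window, and Protocol 13 defers detail to the SAP.
- *These harms vanish from the report.* They do not. All AEs and all SAEs are listed, sorted by treatment group. Worsening after Day 0 and most onsets with a missing day are tabulated, and disposition can show a withdrawal. SAEs are also reported within 24 hours, and the data monitoring committee reviews accruing data. What is missing is a by-arm rate.
- *The treatment-emergent window should simply start at the first steroid dose.* Moving the Appendix 3 start date as well, while related-event tables keep a surgery-day window, would impute related events with a missing day to Day -2. They would then drop out of tables that now count them. A new window alone would also still omit a subject who takes steroid but never receives vector.

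The remaining objection is that two days are little against 12 months of follow-up. That is fair, and it limits the importance of the point. It does not supply the missing rate, since a listing gives none.

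**Conclusion.** The point holds as a minor gap in safety reporting. AEs that start between the first required steroid dose and surgery, and do not worsen after Day 0, are in general left to listings. Only treated subjects are exposed to the steroid in that interval, so omitting steroid-caused events can only lower the treated-arm rates. The by-arm tables can therefore slightly understate the harms of the full regimen.

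The part left out is 2 of 21 steroid days, both at the highest daily dose level. The number of events is unknown; under assumed rates of 0.5% to 5% it would be about 0.5 to 4.8 of 96 planned treated subjects. No bias of any particular size is shown, and the effect is probably small.

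The two-day figure assumes surgery on the planned date. The steroid is timed from that date, while Day 0 in treated subjects is the actual date of surgery, so a postponement after the steroid has started could lengthen the uncounted interval.

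**What to change.** Keep the surgery-day treatment-emergent definition and the Appendix 3 date rules unchanged. Add to SAP 11.1 one by-arm summary of AEs and SAEs, by SOC and PT, with onset:

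- in treated subjects, from the first protocol-required corticosteroid dose up to surgery;
- in controls, from two days before Visit 2 (Day 0) up to Day 0;
- in a subject who starts steroid but never receives vector, from first steroid dose to study exit.

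Base the table on all randomised subjects, so that the last group is included. Because the interval can differ between subjects, a footnote with the subject-days per arm would help the reader.

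The cost is one extra table, which will include a few incidental pre-operative events. Steroid compliance is already captured in the diary card and eCRF (Protocol 9.8). No change to the steroid regimen is implied.
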